Until now, laser lithotripsy during ureteroscopy (URS) has been performed using Holmium: yttrium-aluminum-garnet laser. Recently, a new Thulium laser has been introduced. The pulsed infrared light emitted by the Thulium laser has a wavelength of 1940 nm which is close to the water absorption peak, and the energy delivered by the Thulium laser is therefore highly absorbed by water. High water absorption corresponds to low threshold for tissue ablation and stone lithotripsy ¹. The Thulium laser is therefore expected to be very efficient at disintegrating stones. Previous studies have predicted Thulium laser lithotripsy to be up to four times faster than Holmium laser lithotripsy using the same energy settings ². In theory, as the threshold for tissue ablation is low, ureteral lesions caused by unintentional laser firing at the mucosa may result in less bleeding than with holmium lasers as bleeders are instantly coagulated. In addition, the Thulium laser has the advantage of having smaller laser fibers enabling better irrigation during URS.

As the first hospital in Europe, HUH got access to the new Olympus Soltive Premium SuperPulsed Thulium Laser System in June 18th 2020. To date, approximately 30 procedures have been performed using this laser at our hospital, and the preliminary results seem promising.

The laser has been shown to be a highly efficient tool in the treatment of both ureteral and renal stones even at very low energies. Stone burden up to 3.2 cm has been effectively cleared. Our impression is that the laser produces significantly smaller fragments and finer dust-particles compared to the Holmium laser in shorter time. Fragmenting at a setting of 0.6 - 0.8 J at 30 Hz (18 - 24 W) produces dust and disintegrates stones faster than dusting at 0,1 - 0,2 J at 200 - 240 Hz (20 - 48 W), even though the latter setting results in finer dust. Complete disintegration of a 1 cm stone at 0,6 J at 30 Hz has been achieved in less than 20 minutes.

A remarkable characteristic noted when breaking ureteral stones at low energy, is the absence of retropulsion.

No significant intraoperative complications have been registered so far. However, in a few cases small superficial mucosal laser lesions were noted. No bleeding impairing endoscopic vision has been registered, and adequate vision was maintained in all without the use of irrigation pumps. Insertion of a JJ-stent post endoscopically also seems to be required in a few cases only.

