Although the preliminary results of the new Thulium laser look promising, there are no clinical randomized trials comparing it to the Holmium laser, which is the current standard laser used for URS lithotripsy.

Aims of the study:

The primary aim of the study is to compare the stone free rate (SFR) following URS lithotripsy with Holmium and Thulium lasers. SFRs will be compared both for ureteral stones, renal stones and ureteral and renal stones in total.

Secondary aims are to compare the results of the two lasers in terms of operating times, intraoperative complications, postoperative complications and the rate of post endoscopic JJ-stenting.

Hypothesis:

1. The SFR, defined as no residual fragments detected on CT scan 3 months after the URS, is higher following lithotripsy with Thulium laser compared to Holmium laser. The corresponding H_0 is that "*there is no difference in SFR following laser lithotripsy with the two lasers.*"
2. Operating time following Thulium laser lithotripsy is shorter compared to Holmium laser. H_0 : "*There is no difference in the operating time between the two laser machines.*"
3. There are less intraoperative complications during Thulium laser lithotripsy compared to Holmium laser. H_0 : "*There is no difference in intraoperative complications between the two laser machines.*"
4. There are less postoperative complications (infections, readmissions, strictures) during Thulium laser lithotripsy compared to Holmium laser. H_0 : "*There is no difference in postoperative complications between the two laser machines.*"
5. Fewer patients will need post endoscopic insertion of JJ-stent following Thulium laser lithotripsy compared to following Holmium laser lithotripsy. The corresponding H_0 is that "*there is no difference in the frequency of post endoscopic JJ-stent placement following laser lithotripsy with the two lasers.*"

Study design:

The study is planned performed as a prospective randomized trial. All patients ≥ 18 years scheduled to URS lithotripsy at the day surgery unit at HUH are invited to be enrolled in the study. After written informed consent, patients are randomized to URS lithotripsy with either Holmium laser or Thulium laser.

Randomization:

The randomization is performed electronically with the same number of patients in each group. The results of the randomization are being kept in sealed and consecutively numbered envelopes that is opened just before starting the endoscopic procedures in each patient.

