Patients and data sampling:

All patients ≥ 18 years scheduled for URS lithotripsy at the day surgery unit at HUH are basically eligible for inclusion in this study. Patients with either ureteral stones, renal stones or both can be included. The number of patients/procedures needed to be included in the study is specified in the Power analysis-section below.

The following data need to be registered:

- *Preoperative status:* Age, sex, ASA-status, indication for surgery, earlier surgery for same stone, stone status, acute/planned surgery, prestenting-status, infection.
- *Peroperative characteristics:* Randomization status, primary surgeon, antibiotic prophylaxis, operating time, need for safety guide wire and access sheath, type of endoscope (semi-rigid/flexible), balloon dilatation, impacted stone, successful access to the stone, laser modality, laser settings, laser time and energy used, dusting or fragmentation, retrieval of fragments or left for spontaneous passage, surgeon's assessment of post

- endoscopic stone free status, complications, placement of JJ-stent.
- *Postoperative status:* Length of hospital stay, immediate complications that need urgent treatment, complications after discharge requiring readmission, 3-months follow-up with CT scan (SFR, stricture rate).

The data will be plotted in a registration form which will be available both electronically and on paper. If paper form is used, the data will be registered electronically subsequently and the paper-form maculated. Completed registration-forms are transferred to a SPSS database for statistical analyses.

The registration-forms and the database will be stored at Helse-Bergen's scientific and research server in a designated file assigned from the Data Protection Officer. An ID-Key file combining personal ID to the registration form will be stored at a designated server for this purpose at Helse-Bergen's research servers. Only the project manager ([name]) will have access to this ID-Key file.

The registration forms and the ID-Key file will be kept on the server for five years after the study has been completed in accordance with the law. After five years the data will be made anonymous in terms of deleting the ID-Key file.

Power analysis:

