In an earlier study, we found the 3-months SFR after Holmium laser URS lithotripsy to be 54.2% using a strict definition of *no* residual fragments detected on CT scan³. Although this is a strict definition, it leaves no room for personal judgement whether a patient is stone free or not. The definition is therefore suitable for this study purpose.

We expect the Thulium laser to be more efficient in clearing stones than the Holmium laser, with a total SFR of around 80% after URS lithotripsy using this laser.

Comparison of the SFRs between Holmium and Thulium laser will be done using the χ^2 -test. An effect size of 0.3 is considered appropriate assuming the SFRs after Holmium and Thulium laser lithotripsy to be 54.2% and 80%, respectively. The α error probability is set to 0.05 and the power (1- β error probability) is set to 0.8. Comparison of the SFRs following URS with the

two lasers with χ^2 -test is based on a 2 x 2 table, and in this case with only 1 degree of freedom (Df).

Using G*Power, version 3.1.9.4 for power analysis, the total sample size is calculated to be 88. To compensate for possible non-evaluable patients, a total of 120, i.e. 60 patients in each group, are planned to be included in the study.

Statistical analyses:

Statistical analyses will be performed using IBM SPSS Statistics 25 or higher (IBM, Armonk, NY). A p -value < 0.05 will determine statistical significance.

Continuous variables will be compared using independent-samples t -tests, or in the cases where a normal distribution is not met, Mann-Whitney U test. Exact chi-squared test and Fisher's Exact test are used comparing categorical variables.

Ethical considerations, ethical approval and patient consent

Holmium laser lithotripsy is the gold standard during URS today and is in use worldwide. Preliminary results with the new Thulium laser seem promising, however, no randomized trials comparing the outcome of the two laser modalities exists. The planned study therefore seems to be highly clinically relevant. In addition, the new Thulium laser is approved for use during endoscopic lithotripsy and the patients should therefore not be exposed to extra risk of harm using this laser.

Applications for approval by The National Committees for Research Ethics in Norway and The Data Protection Authorities at HUH will be sent prior to study start. In addition, the study will be registered in the clinical research database for randomized trials, ClinicalTrials.gov.

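### All stone-free-rate comparisons are planned as unadjusted 2 x 2 tests; prespecifying adjustment for preoperative stone size would cheaply recover some power and precision, by an amount the documents do not fix

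*Combined protocol and SAP*

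**What the plan says.** Aims of the study sets three comparisons within the primary aim: "SFRs will be compared both for ureteral stones, renal stones and ureteral and renal stones in total". Power analysis names a chi-squared test for SFR and explains that the comparison of the "two lasers with χ^2 -test is based on a 2 x 2 table, and in this case with only 1 degree of freedom (Df"). Statistical analyses adds exact chi-squared and Fisher tests for categorical variables. No covariate, regression model or stratified test appears anywhere, and Randomization describes equal group sizes but no stratification.

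Patients and data sampling admits adults scheduled for ureteroscopic lithotripsy with ureteral stones, renal stones or both, and gives no size limit. The preoperative items to be registered are "Age, sex, ASA-status, indication for surgery, earlier surgery for same stone, stone status, acute/planned surgery, prestenting-status, infection". Size is not named among them. The allocation envelope is opened just before the procedure. On the spread of stone size, the background text offers a 1 cm stone and the remark "Stone burden up to 3.2 cm has been effectively cleared".

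The sample size rests on this sentence: "An effect size of 0.3 is considered appropriate assuming the SFRs after Holmium and Thulium laser lithotripsy to be 54.2% and 80%, respectively".

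**The concern.** The endpoint is strict: one residual fragment on the 3-month CT is a failure. The amount of stone present at the start is the natural baseline counterpart of that outcome, and eligibility lets it vary widely. Neither the randomisation nor the analysis makes use of it.

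This matters somewhat more for the two location-specific comparisons. They use only part of the 120 patients, and within one location adjusting for location can explain nothing, so size is the obvious baseline variable left. If size predicts clearance, a crude 2 x 2 test leaves explainable variation in the comparison and gives up power and precision that need no extra patients to recover.

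**Working it through.** **Inputs from the documents.** SFR 54.2% (Holmium) and about 80% (Thulium); effect size w = 0.3; alpha 0.05; power 0.8; calculated total 88; planned total 120, 60 per arm.

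**Inputs that must be assumed.** The documents do not give the strength of the relation between size and SFR, the share of patients in each location, or SFRs by location (80% is given only as a total). I apply 54.2% vs 80% throughout, take a location subgroup to be half the sample, and let the odds ratio per SD of log size be 1.5, 2.0 or 2.7.

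**Step 1: the plan's own figure.** For a 1-df chi-squared test the noncentrality is N·w² = 88 × 0.09 = 7.92. Power ≈ Φ(√7.92 − 1.96) = Φ(0.854), about 80.4%. The stated 88 is reproduced.

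**Step 2: crude power at the stated SFRs.** The mean SFR is 0.671, so w = 0.258 / (2·√(0.671 × 0.329)) = 0.275, slightly below 0.3. With power ≈ Φ(w·√N − 1.96):

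- N = 44 (half of 88): 44.5%
- N = 60 (half of 120): 56.6%
- N = 88: 73.1%
- N = 120: 85.3%

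**Step 3: effect of adjustment, by simulation.** Log size is standard normal. A logistic outcome model is calibrated so that the marginal SFRs stay at 54.2% and 80%. The crude Pearson chi-squared is compared with a logistic score test for laser arm adjusted for log size.

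| Per arm | Crude | OR 1.5 | OR 2.0 | OR 2.7 |
|---|---|---|---|---|
| 22 (half of 88) | about 44% | 46% | 50% | 50% |
| 30 (half of 120) | about 57% | 60% | 61% | 65% |
| 44 (all of 88) | about 75% | 76% | 78% | 81% |
| 60 (all of 120) | about 87% | 88% | 90% | 92% |

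Repeat runs differ by one or two points, so the table should not be read more finely than that. With no prognostic effect there is no gain at 44 or 60 per arm, and one to two points at 22 to 30 per arm that come only from the test being slightly liberal there. Null rejection was about 5 to 6% for the adjusted test.

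**Step 4: check by hand.** Averaged over the two arms, these odds ratios correspond to within-arm correlations between size and outcome of about 0.17, 0.29 and 0.38. Replacing N by N/(1 − r²) in the Step 2 formula gives:

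- N = 60: 57.9 / 60.3 / 63.3% (crude 56.6%)
- N = 120: 86.3 / 88.2 / 90.2% (crude 85.3%)

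The gains agree with the simulation to within about two points.

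**Step 5: chance imbalance.** At 30 per arm, the standard error of the difference in mean size is √(2/30) = 0.26 SD. An imbalance of that size shifts the crude SFR difference by about 2 to 6 points for odds ratios from 1.5 to 4.5 per SD. The planned difference is 80 − 54.2 = 25.8 points.

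**The case against.** The strongest objection is that the premise is not in the documents. Nowhere do they say that stone size predicts the 3-month SFR. The background remarks show a range of sizes, not a relation with clearance. This stands: the gain can be given only as an assumed range that includes almost nothing.

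Second, the quoted 2 x 2 sentence belongs to the sample-size text for the total comparison. That is true, but no other SFR test is given for either location, so it and the exact tests are all the plan offers.

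Third, the planned total of 120 already has crude power of about 87% if everyone is evaluable. This also stands: adjustment then adds only about 1 to 5 points.

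Three stronger readings are tempting but are not supported:

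- *That the crude test is biased if one arm happens to receive larger stones.* Under randomisation such an imbalance is random error, already allowed for in the test's type I error.
- *That adjustment would rescue the location comparisons.* Halving the sample takes power from about 87% to about 57%; adjustment brings back only a small part of that.
- *That stone size is already available as a pre-randomisation covariate.* The plan lists only an undefined stone-status item, and the registration form is not part of the documents.

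A practical objection also has weight. At 22 per arm about 22 × 0.2 = 4.4 Thulium failures are expected, which is thin for a logistic model. The model must stay at one covariate and have a fallback.

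**Conclusion.** The point holds as a cheap improvement in efficiency. It does not show that the planned test is invalid. The primary-aim SFR comparisons ignore the baseline variable most closely tied to the definition of success.

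For odds ratios of 1.5 to 2.7 per SD of log size, the gain is about 3 to 8 points of power at 30 per arm, 2 to 6 at 22, 1 to 6 at 44 and 1 to 5 at 60. One to two points of the gain at 22 to 30 per arm reflect the slightly liberal small-sample test. If size is weakly prognostic the gain is close to zero.

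A reader might infer losses of around 15 points (57% against 72% at 30 per arm). That figure needs an odds ratio of about 4.5 per SD, for which the documents give no basis.

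All these figures assume that 54.2% vs 80%, and the same strength of size effect, hold within each location, and that each location holds half the patients. On those assumptions neither location comparison reaches 80% power over this range, with or without adjustment.

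**What to change.** In Statistical analyses, prespecify that each SFR comparison (ureteral, renal, total) uses a logistic model with laser arm and log preoperative stone size as the only covariate. Name in advance either the score or the likelihood-ratio test. Report the standardised (marginal) SFR difference with 95% CI. Keep the crude 2 x 2 or exact test as a sensitivity analysis, and make it the stated fallback if failures are too few to fit the model.

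In Patients and data sampling, state that the stone-status item includes size in mm, entered before the envelope is opened. For patients with both ureteral and renal stones, state that the location-specific models use the size of the stones in that location and that the total model uses cumulative size.

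The cost is a few lines of text and one numeric field, with no extra patients, visits or scans. There are two small downsides: the model yields a conditional odds ratio, so the SFR difference has to be standardised from it, and size must be recorded as a number for every patient. The adjustment has to be fixed before outcome data are seen; choosing it afterwards would undermine it.

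### Operating time (Hypothesis 2) is compared without baseline adjustment and with the effect measure left open; one prespecified adjusted model would gain precision at almost no cost

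*Combined protocol and SAP*

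**What the plan says.** The combined protocol and SAP makes operating time a secondary endpoint (Aims of the study: "Secondary aims are to compare the results of the two lasers in terms of operating times"). Hypothesis 2 is directional ("Operating time following Thulium laser lithotripsy is shorter compared to Holmium laser"), and its null is "There is no difference in the operating time between the two laser machines".

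The Statistical analyses section covers every continuous outcome in one sentence: "Continuous variables will be compared using independent-samples t -tests", "or in the cases where a normal distribution is not met, Mann-Whitney U test". The threshold is "A p -value < 0.05 will determine statistical significance". No covariate, regression or stratified test is named. No criterion for normality is given, and nothing says which of the two tests applies to operating time.

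Patients and data sampling admits adults with ureteral stones, renal stones or both. The Randomization section describes equal groups and mentions no stratification. The split by stone location in Aims of the study is planned for the stone free rate only. The preoperative items include "earlier surgery for same stone, stone status, acute/planned surgery, prestenting-status, infection"; stone size and location are not named separately.

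**The concern.** Stone size and location are natural predictors of how long a ureteroscopy takes, and the documents point that way without giving a figure. The opening background text mentions stone burdens up to 3.2 cm and ties a disintegration time to a stone size ("Complete disintegration of a 1 cm stone at 0,6 J at 30 Hz has been achieved in less than 20 minutes"). The Laser settings section gives different start-up power for ureteral and renal stones.

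If such predictors are left out, the variation they explain stays in the error term. The confidence interval is then wider than it need be, and a real time saving is easier to miss.

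A second weakness is that the observed times decide whether the trial compares means or ranks. The effect to be reported is therefore not settled beforehand, and the undefined criterion leaves room for discretion.

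**Working it through.** **The plan's own figure.** The only stated sample size is 88 for the stone free rate (w = 0.3, 1 df, α 0.05, power 0.80). It reproduces: ((1.960 + 0.842)/0.3)² = 87.2, and 88 patients give power 0.804. It does not bear on operating time, for which the plan states no SD, target difference or power.

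**Inputs.** From the documents: 60 per arm (Power analysis) and a 0.05 threshold, taken as two-sided. Operating time is recorded at surgery, so 60 per arm is used throughout. Assumed, because the documents give nothing: log-normal times, SD of log time 0.55, and a correlation r of 0.2 to 0.7 between log stone size and log time.

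**Step 1: what the unadjusted test can detect.** Detectable difference at 80% power = (1.960 + 0.842) × √(2/60) = 0.511 SD. This needs no assumption about the SD itself.

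**Step 2: effect of adjustment.** A baseline covariate with correlation r multiplies the standard error by √(1 − r²). The equivalent sample-size factor is 1/(1 − r²).

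**Step 3: power for a 20% shorter time, by formula.** |ln 0.80| = 0.223. SE unadjusted = 0.55 × √(2/60) = 0.1004, so z = 2.22 and power = Φ(2.22 − 1.96) ≈ 60% for an unadjusted t-test on log time. The adjusted SEs follow from Step 2. The simulation column gives the results for the adjusted log-time model, across repeated simulations where these differ.

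| r | SE | Power, formula | Power, simulation | Equivalent extra patients | Detectable difference |
|---|---|---|---|---|---|
| 0.2 | 0.0984 | 62% | about 61% | 4% | 0.501 SD |
| 0.3 | 0.0958 | 64% | 63-65% | 10% | 0.488 SD |
| 0.5 | 0.0870 | 73% | 72-74% | 33% | 0.443 SD |
| 0.7 | 0.0717 | 87% | 85-86% | 96% | 0.365 SD |

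The planned rule (simulated as a Shapiro-Wilk pre-test, then t-test or Mann-Whitney on raw times) had about 57% power. An unadjusted t-test on log time reached 58-61%, so most of the gain comes from the covariate and little from the log scale.

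**Step 4: larger effects.** For a 25% shorter time, the planned rule has about 79-81% power, against 86% (r = 0.3), 91% (0.5) and 98% (0.7) adjusted. For a 30% shorter time, planned power is about 93%, against 94-96% (r = 0.2-0.3) and 98% (r = 0.5).

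**Step 5: does the switching rule inflate type I error?** With 8,000 simulated null trials at 60 per arm:

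| Distribution of times | Type I error | Switched to Mann-Whitney |
|---|---|---|
| Normal | 0.049 | 10% |
| Log-normal, SD 0.3 | 0.048 | 88% |
| Log-normal, SD 0.5 | 0.053 | 99.9% |
| Log-normal, SD 0.7 | 0.050 | 100% |

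The error rate stays near 5%. With skewed times the likely outcome is a rank test, for which the plan specifies no effect estimate.

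**The case against.** The strongest reply is that omitting adjustment for a secondary endpoint with no power target is not an error. Randomisation makes the unadjusted comparison valid, and its p-value already allows for chance imbalance. The stone free rate and the sample size are untouched. All of this stands.

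The reply also says that the benefit is undocumented, and this stands too. A reader might infer from the background text that operating time depends strongly on stone size. The documents do not show that: they give one upper stone burden and one disintegration time at one laser setting, which is not operating time. Other recorded items, such as surgeon, access sheath, impaction and stenting, may contribute as well. At r = 0.2-0.3 the gain is only a few points of power, and for a large time saving the planned test is already adequate.

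A reader might also infer that choosing the test from the data invalidates the p-value, or that unadjusted times are biased. Step 5 does not support the first, and randomisation answers the second. Nor does Mann-Whitney prevent medians in minutes from being reported; the plan simply does not say what will be reported.

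Finally, a single adjusted ratio may hide a difference by location. The Laser settings section gives separate Holmium and Thulium start-up settings for renal stones but one setting for ureteral stones, and it expects greater efficiency for Thulium in renal stones. This objection is fair, and the fix takes it into account.

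None of this is a reason to leave the estimand open, or to forgo precision that needs no extra patients or procedures.

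**Conclusion.** The point holds as one of efficiency and prespecification on a secondary endpoint. It is not a point about bias or false positives. Any true correlation appreciably above zero makes the planned analysis less precise than an adjusted one.

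The size of the loss is an assumption. For a 20% shorter time it runs from a few points of power at r = 0.2 to nearly 30 at r = 0.7, and it shrinks as the true effect grows. These figures rest on log-normal times, an SD of log time of 0.55 and 60 patients per arm, with size as the only covariate. The absence of a fixed effect measure follows from the text alone and needs no assumption. The change is worth making because it is cheap, but it has to be fixed before the outcome data are seen to carry weight.

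**What to change.** In Statistical analyses, replace the general rule, for operating time only, by one prespecified model: linear regression of log(operating time) on randomised arm, log preoperative stone size and preoperative location (ureteral, renal, both). Fix one size measure in advance, for example the sum of the largest diameters of the target stones.

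Report the Thulium/Holmium ratio of geometric means with a 95% CI. Show the ratio by location descriptively. Keep the unadjusted test as a sensitivity analysis, and state which test it is.

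In Patients and data sampling, name stone size and stone location explicitly under stone status.

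The cost is a few lines of analysis text and two explicit entries on the registration form, with no extra patients or procedures. The small downside is that the main result is a ratio of times and not a raw difference in minutes.

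### The exact tests planned for the complication comparisons (Hypotheses 3 and 4) are valid but conservative; Boschloo's test recovers some power at no cost in error control

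*Combined protocol and SAP*

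**What the plan says.** Statistical analyses has one sentence on categorical outcomes: "Exact chi-squared test and Fisher's Exact test are used comparing categorical variables". The threshold for every comparison is "A p -value < 0.05 will determine statistical significance". The plan does not say when each exact test applies, and it names no mid-p or unconditional exact version.

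Hypothesis 3 is that "There are less intraoperative complications during Thulium laser lithotripsy compared to Holmium laser". Hypothesis 4 says the same of postoperative complications (infections, readmissions, strictures). Each null hypothesis is one of no difference, so I read the tests as two-sided; sidedness is not stated.

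The sample size comes from the primary endpoint, the stone free rate (SFR), which Power analysis assigns to a χ² test. The outcome there is that "a total of 120, i.e. 60 patients in each group, are planned to be included in the study". The plan gives no expected complication rate and no power for Hypotheses 3 and 4. The nearest information is in the background section, on about 30 Thulium procedures: "No significant intraoperative complications have been registered so far". The same section mentions small superficial mucosal lesions in a few of them.

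**The concern.** Fisher's test and the exact chi-squared test both condition on the total number of events. With equal arms and few events, few tables are possible, and the true type I error can lie far below the nominal 5%. A test that uses only part of its allowed error gives up power.

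Hypotheses 3 and 4 are the plan's formal comparisons of complications, and the trial was not sized for them. If power can be recovered within the same 5% limit and without more patients, the plan should take it. The choice has to be made in advance, because changing the test after seeing a p-value just above 0.05 would not be credible.

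**Working it through.** **Inputs.** 60 per arm and 1:1 allocation (Power analysis, Randomization); 44 per arm as a check (half of the calculated 88); alpha 0.05, taken as two-sided. Event rates are my assumptions, shown over a range.

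**The plan's own figure.** The plan states no size or power for the complication endpoints, so only the SFR sample size can be reproduced. Noncentral chi-squared, 1 df, λ = N·w², w = 0.3, alpha 0.05: N = 87 gives power 79.9% and N = 88 gives 80.4%. The stated 88 is confirmed.

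**Method.** Let a and b be the numbers of patients with an event in the two arms. For a test with rejection region R, the rejection probability is

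Σ over (a, b) in R of Bin(a; 60, p₁) · Bin(b; 60, p₂),

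summed over all 61 × 61 tables. With p₁ = p₂ this is the true type I error; otherwise it is power.

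- Fisher: R is the set of tables with two-sided p < 0.05. With equal arms the exact chi-squared test has the same region, so the second named test changes nothing.
- Boschloo: R is the set of tables whose two-sided Fisher p is at or below the largest cut-off that keeps the maximum type I error, over all common rates, at or below 5%. At 60 per arm the cut-off is 0.0665.

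**True type I error, 60 per arm (%)**

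| Common rate | Fisher | Boschloo |
|---|---|---|
| 3% | 0.32 | 1.22 |
| 5% | 1.05 | 2.66 |
| 10% | 2.18 | 3.38 |
| 20% | 2.82 | 3.96 |
| 30% | 3.08 | 4.13 |
| Maximum over all rates | 3.53 | 4.89 |

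**Power (%)**

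| Assumed rates | Fisher, 60 per arm | Boschloo, 60 per arm | Fisher, 44 per arm | Boschloo, 44 per arm |
|---|---|---|---|---|
| 10% vs 2% | 27.7 | 39.5 | 14.3 | 24.5 |
| 15% vs 3% | 52.0 | 60.9 | 34.9 | 45.0 |
| 20% vs 5% | 62.7 | 67.9 | 46.6 | 53.9 |
| 20% vs 10% | 24.7 | 29.0 | 17.4 | 22.8 |
| 10% vs 5% | 8.8 | 13.4 | 5.4 | 9.4 |

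**Dominance.** At 60 per arm every table that Fisher rejects is also rejected by Boschloo, and Boschloo rejects 72 more. These include 5 vs 0 (Fisher p = 0.057), 7 vs 1 (0.061) and 9 vs 2 (0.053).

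**Example, 7/60 vs 1/60.** Given 8 events in total, the probability of 0 in one named arm is C(60,8)/C(120,8) = 0.0030, and of exactly 1 is 60·C(60,7)/C(120,8) = 0.0276. The two-sided Fisher p is 2 × (0.0030 + 0.0276) = 0.061. Boschloo gives p = 0.042. Doubling the one-sided Boschloo p gives the same value: 2 × 0.0211 = 0.042.

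**A software trap.** scipy's Boschloo function expects the arms as columns. With the arms entered as rows, the same data return 0.030, because the wrong margin is held fixed. That figure is not a valid alternative p-value.

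**The case against.** **Nothing in the plan is invalid.** This is correct. Five per cent is a ceiling, and Fisher's test respects it. A reader might infer from a true error of 0.3% that the plan's error rate is mis-set or that its test is wrong. The documents do not support that: the plan promises a threshold of 0.05, and the named tests keep to it.

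**Low rates are assumed.** This also stands. A reader might infer that complications are known to be rare here. The documents give no rate for either arm. The background remark covers only significant intraoperative events with Thulium, and it says nothing about Holmium or about Hypothesis 4. Even zero events in 30 is compatible with a rate of up to 1 − 0.05^(1/30) = 9.5% (one-sided 95% limit), and the mucosal lesions might count as events. However, Fisher's error is still only about 3% at a common rate of 30%, so the conservatism does not depend on rare events. Its degree does.

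**The main limit is the sample size.** This stands. The larger gains need four- to five-fold differences in rates. For 20% vs 10% or 10% vs 5% the gain is 4 to 5 points, and for 15% vs 10% it is about 2 (7.8% to 10.0%). A reader might infer that a change of test would give the trial adequate power for harm. It would not: no scenario above exceeds 68%.

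**Easier rejection also helps a claim of benefit.** Hypotheses 3 and 4 predict fewer complications with Thulium, and the plan states no multiplicity adjustment for its five hypotheses. The first part is true, but Boschloo's test is two-sided and controls each comparison at 5%, which is the guarantee that the plan already offers. Multiplicity is a separate matter.

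**The endpoint may not be a single yes/no variable.** This stands as a limit of scope. The plan does not define either complication endpoint as one binary outcome, and the point applies only where it is analysed that way.

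**Conclusion.** The point holds as a cheap improvement. For patient-level yes/no complication outcomes at 60 per arm, the planned exact tests have a true two-sided error of about 0.3% to 3.1% at assumed common rates of 3% to 30%, and at most 3.5% at any rate. Boschloo's test stays at or below 4.9%, loses no rejection that Fisher's test makes, and adds about 4 to 12 points of power in the tabulated scenarios at 60 per arm.

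This rests on assumed event rates, equal arms, two-sided testing and a binary definition of each endpoint. It concerns Hypotheses 3 and 4 only and does not touch the χ² test planned for SFR. The complication comparisons stay underpowered whichever test is used.

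**What to change.** In Statistical analyses, add one sentence before any results are seen: patient-level yes/no comparisons for Hypotheses 3 and 4 use Boschloo's unconditional exact test, two-sided at 5%, with tables ordered by the two-sided Fisher p-value and the treatment arm sizes as the fixed margins, in place of the exact chi-squared and Fisher tests. If scipy is used, add that the arms are entered as columns.

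The cost is that sentence and a few lines of code. SPSS is the stated package, so the test may have to be run in other, free software, and some readers will know it less well than Fisher's. It needs no extra patients or data.
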